Phase 2 will examine the subjective effects (appeal) of menthol vs. non-menthol cigarettes (own brand) as they occur in the participant's natural environment. To achieve this aim (objective), participants will engage in 14 days of twice-daily ecological momentary assessment (EMA). Following Phase 1 (if recruited during normal operating procedures), participants will complete 14 days of EMA of smoking behavior and subjective response (satisfaction, craving reduction, psychological reward, sensory effects like throat hit) twice a day, smoking as usual. NOTE: If participants are enrolled when there are COVID-19 restrictions on in-person data collection, they will begin the daily EMA after they complete the baseline survey, and before they attend the 3-person visit lab visits. Participants will answer a set of questions about their smoking behavior by responding to a series of survey questions that will be deployed on an app installed on their phone (or a study provided phone if their phone is not compatible with the app. The app is only available only on the Android platform). Phones will be mailed back to the study lab at the end of the 14day monitoring period using a pre-addressed stamped envelope provided by the study team. Prompts (e.g., notifications to the telephone) will be programmed to occur at random times within each of two 4hour time blocks, one corresponding to the morning and one the evening. Prompts will be programmed to coincide with respondents' sleep-wake cycle (i.e., the usual time they wake up and go to bed). Sleep/wake cycle will be collected at the baseline visit. At the completion of EMA, participants will be

asked to participate in a brief assessment to query about satisfaction with and reactivity to the EMA assessments. They will get paid \$15 for this survey. EMA entries are expected to last ~5 minutes (based on response times in prior studies). Participants who miss EMA surveys or the EMA reactivity survey will be given the opportunity to complete the surveys by invitation via REDCap.

Phase 3 Overview and Experimental Design

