In addition to the aforementioned recruitment methods, we will use BuildClinical, who will assist with recruitment by designing and managing targeted, GCP-compliant, IRB approved advertising. **BuildClinical** is a data-driven software platform that helps academic researchers recruit participants for research studies more efficiently using social media, software, and machine learning. BuildClinical utilizes study-specific advertisements to engage participants on digital platforms such as Facebook, Google, WebMD, etc., and redirect them to a study-specific landing page should they click it. On the landing page, the person can complete an online pre-screen questionnaire that gets routed into BuildClinical's platform. BuildClinical's Secure Socket Layer (SSL) software, which encrypts all inputted information, keeps participant information private and HIPAA compliant. BuildClinical's backend servers are stored in the USA at some of the most secure data centers in the world. The study team will access BuildClinical's platform to review and select qualified screening participants for additional screening. Interested individuals may then choose to enroll in the study by completing Informed Consent and HIPPA prior to scheduling a baseline lab or virtual session.

We have included the BuildClinical advertisement materials, pre-screening questionnaire, and study information landing page design and

IRB NUMBER: 10581
B NUMBER: 10581
IRB APPROVAL DATE: 02/14/2022
PROVAL DATE: 09/13/202112

content.[Inclusion/Exclusion criteria](#)

Inclusion criteria:

- (1) Ages 18 to 26;
- (2) Currently smoke cigarettes "somedays" or "everyday";
- (3) Started smoking "somedays" or "everyday" in the past 12-months or more than 12 months ago.
- (4) A strong preference for menthol or non-menthol cigarettes (i.e., smoke one type $\geq 80\%$ of the time).
- (5) Able to read and understand the informed consent
- (6) Willingness to abstain from nicotine containing products or other combustible products (e.g., smoked cannabis) for at least 12 hours prior to each in-person or virtual laboratory visit (confirmed by CO $\leq 8\text{ppm}$ for each in-person study visit in Phase 1). Will be rescheduled once if CO is not within acceptable range.

Exclusion criteria:

- (1) Current use of nicotine replacement therapy (NRT);
- (2) Currently pregnant or planning to become pregnant, or breast feeding (verified by pregnancy test at each study visit/session);

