All participants will be reimbursed for their participation via cash, gift code, or reloadable gift card. Participants will be compensated using an incentive paradigm to ensure participant retention in all 3 laboratory visits and completion of all daily EMA surveys. Participants will receive \$35 for completing the baseline survey, \$45 for completing the Visit 1 smoking session, \$45 for Visit 2, and \$45 for Visit 3. Participants will be compensated upon return of the smartphone after the 2-weeks of EMA monitoring based on the following compensation schedule: They will receive \$1 for each completed EMA survey (totaling \$28), a \$10 bonus each week for completing all EMA surveys in a week period (totaling \$20), and a \$50 bonus if they complete 85% of the EMA surveys over the courses of two weeks (23/28 surveys). Participants can therefore be eligible to receive a total of \$98 if they complete all EMA surveys.

There will be a brief post-EMA survey to assess reactivity, for which they will be paid \$15 and then a 6month follow-up for which they will be paid \$55. Participants will be compensated \$15 each for

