Patterns of missing data, attrition rates, distributional properties of dependent and other measures, and correlations among all measures will be assessed. We will control for potential variables related to missing data and utilize multiple imputation methods (expectation maximization algorithm). Analysis of EMA data will use hierarchical linear modeling (HLM, which provides flexibility in handling missing data such that robust estimates can be obtained even when data are missing at random (MAR). Models for Aim 2 will examine effects of cigarette type (menthol vs non-menthol) at the day-level on predictions of subjective response (satisfaction, reward, craving reduction, physical sensations like throat grab) in that same smoking episode, and subjective response at time t (e.g., morning) predicting smoking behavior (number of cigarettes, any smoking, craving) occurring at subsequent points in time to determine the impact of subjective response on continued use by menthol status (controlling for cigarette consumption and subjective response from the previous report). A sub-group of respondents may have fixed (unchanging) ratings of subjective response over the course of 14 days, although this is unlikely given our pilot study data suggesting that daily subjective response varies significantly in this age group. We will examine baseline and daily factors that set “no changers” apart from those whose show fluctuations in subjective response. These factors will be used as covariates in models. Within-person slopes capturing associations between cigarette type and subjective response will be saved and used in Aim 3 regression models to predict 6-month smoking outcomes. Covariates with $p < .05$ will be retained in final models.

Analyses will control for the order in which study phases were completed (e.g., Phase 1 vs Phase 2 first).

Phase 3/Aim 3 Analyses

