The main outcome analyses for Aim 3 will examine the predictive validity of laboratory (Phase 1) and EMA (Phase 2) outcomes on changes in the 6-month outcomes of interest, and the degree to which laboratory and EMA ratings of appeal/reinforcement account for (i.e., mediate) the association between menthol brand preference at baseline and smoking behavior change. Hierarchical regression models (continuous or binary logistic) will predict the 6-month outcome of interest, controlling for baseline levels of the outcome in interest and relevant demographics (gender, race/ethnicity, age of smoking onset) in Step 1, baseline menthol status in Step 2, and then laboratory or EMA-derived slopes Step 3. Models will be conducted separately using Phase 1 and Phase 2 measurements of appeal/reinforcement. Mediation will be reflected by a reduction in the association between baseline menthol preference and smoking outcomes after including the requisite measure of appeal/reinforcement in the model. Covariates with $p < .05$ will be retained in final models.

Exploratory analyses will examine changes over time in tobacco use behavior from baseline, 2,4, and 6-months. All data collected during the course of the study, survey and bio-specimen results, will be maintained for future use in cross-reference against new and continued data collection.

Human Subjects Protection

Potential Risks

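### The EMA term named at Aim 3 Step 3 is a within-person cigarette-type slope; single-type reporters carry no information on it, and the plan settles neither the mediator nor the slope model

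*Combined protocol and SAP*

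**What the plan says.** - **Phase 2/Aim 2 Analyses.** Subjective response is modelled on the type of the most recent cigarette in a hierarchical linear model (HLM), and "Within-person slopes capturing associations between cigarette type and subjective response will be saved and used in Aim 3 regression models".
- **Phase 3/Aim 3 Analyses.** The regression enters covariates, then baseline menthol status, and "then laboratory or EMA-derived slopes Step 3". The criterion follows: "Mediation will be reflected by a reduction in the association between baseline menthol preference and smoking outcomes". The same section describes the aim as the degree to which "laboratory and EMA ratings of appeal/reinforcement account for (i.e., mediate) the association", and it refers to Phase 2 measurements of appeal. The slope is the only EMA quantity named as a model term, but the wording is mixed.
- **Inclusion criterion (4).** "A strong preference for menthol or non-menthol cigarettes (i.e., smoke one type" at least 80% of the time. There is no upper limit, so exclusive users qualify.
- **Phase 2 Overview and Experimental Design.** "participants will engage in 14 days of twice-daily ecological momentary assessment (EMA"), and they report "twice a day, smoking as usual". That is at most 14 × 2 = 28 reports, and nothing requires use of both types.
- **What is absent.** The plan gives no rule for participants whose cigarette type never varies, no minimum number of off-type reports, and no statement on whether baseline preference predicts the slope. The Aim 2 text on unvarying participants concerns ratings that do not change, not type. The missing-data text concerns missing reports, not a type that was never smoked.

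**The concern.** A within-person slope on cigarette type needs a person to report both types. The eligibility rule selects people who mostly do not, so the predictor on which the EMA mediator depends has little spread by design.

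The stake is how the EMA mediation result is read. Aim 3 judges mediation by how far the menthol-preference coefficient falls once the mediator is added. A poorly measured mediator makes that fall too small. A null EMA result could then reflect too few off-type reports, not a lack of mediation. The laboratory mediators are modelled separately and are not touched.

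**Working it through.** The documents give no power, variance or effect size for Aim 2 or Aim 3, so there is no planned figure to reproduce. All sizes below are conditional on stated assumptions.

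**1. The identity.** For one person, the variance of the type slope is σ² / Σ(x − x̄)², where x is cigarette type. If x never changes, the sum is 0 and the person's own data do not determine a slope. What is then saved depends on the method:
- Separate per-person regressions give no value.
- HLM with person-centred type gives the model mean.
- HLM with uncentred 0/1 type and uncorrelated random effects gives always-non-menthol smokers the model mean. Always-menthol smokers get a rescaling of their own mean rating.

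None of these contains a contrast between types.

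**2. How many people.** The Compensation section pays a bonus "if they complete 85% of the EMA surveys over the courses of two weeks (23/28 surveys"). I take 24 completed reports, since 0.85 × 28 = 23.8, and treat reports as independent. For off-type share p, P(no off-type report) = (1 − p)^24.

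| Off-type share | P(none) | P(at least 5) |
|---|---|---|
| 0% | 100% | 0% |
| 5% | 29% | 0.6% |
| 10% | 8% | 9% |
| 20% | 0.5% | 54% |

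An equal mix of these four shares gives (1.000 + 0.292 + 0.080 + 0.005)/4 = 34% with no off-type report. The mix is my assumption. With all 28 reports, the proportion reporting one type only is 0.2% if everyone sits at 80% dominant use, and 100% if everyone is exclusive.

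**3. Effect on the planned criterion.** Simulation assumptions:
- 125 people per group, 24 reports each, residual SD 1, variances treated as known.
- Slope = 0.5 × (group − 0.5) plus a person deviation with SD τ.
- Outcome = 0.5 × slope + 0.25 × group + noise with SD 1.

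The true reduction is 0.5 × 0.5 = 0.25. Mean reductions under the equal mix:

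| Saved slope | τ = 0.3 | τ = 0.5 | τ = 1.0 |
|---|---|---|---|
| Known slopes | 0.25 | 0.25 | 0.25 |
| HLM, common mean, centred type | 0.03 | 0.06 | 0.11 |
| HLM, common mean, uncentred type | 0.03–0.04 | 0.06–0.08 | 0.13–0.14 |
| Per-person fits, about 34% dropped | 0.04 | 0.08 | 0.17 |
| HLM, preference predicts slope, centred type | 0.24 | 0.25 | 0.25 |

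In the last row the SD of the reduction is about 0.32/0.15/0.11, against 0.11/0.07/0.07 with known slopes. The bias goes, but the precision does not come back.

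**4. The most favourable eligible case.** Put everyone at 20% off-type. Then Σ(x − x̄)² ≈ 24 × 0.2 × 0.8 = 3.84, and the error variance is 1/3.84 = 0.26. Slope reliability is τ²/(τ² + 0.26) = 0.26/0.49/0.79. Multiplied by 0.25, this predicts reductions of 0.06/0.12/0.20. Simulation with common-mean slopes gives 0.06/0.11/0.20. With everyone at 5% it gives 0.02/0.04/0.10.

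**5. The alternative mediator on the same footing.** Take the mean of 19 preferred-type ratings (24 × 0.8 ≈ 19), a group difference in level of 0.5, and level SDs of 0.3/0.5/1.0. Reliability is τ²/(τ² + 1/19) = 0.63/0.83/0.95, and the simulated reduction is 0.16/0.21/0.24 of 0.25. With lag-1 autocorrelation of 0.5 it is 0.10/0.16/0.22. This measure is also attenuated, but it does not depend on off-type reports.

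**The case against.** - **The mediator may already include rating levels.** Aim 3 speaks of EMA ratings, and Aim 2 secondary outcome (a) is a 14-day aggregate rating by baseline preference. A person-level mean is arguably within scope. This stands as far as it goes: the mediator is unsettled, and it would be wrong to say that the plan allows only slopes. It does not remove the problem, because the slope is the only EMA quantity named at Step 3.
- **HLM copes with sparse data.** It returns a value for everyone, but for a single-type reporter that value holds no contrast between types.
- **The slope need not be abandoned.** This stands. Letting preference predict the slope removes nearly all the bias, whereas the preferred-type mean is a different construct and stays attenuated. The documents do not support a claim that the mean must replace the slope.
- **The bias is not only about single-type reporters.** This also stands. With everyone at 20% off-type, the attenuation is the ordinary effect of an unreliable mediator, and unshrunk slopes share it.
- **The size is unknown.** This is correct. A reader might infer that the slope cannot be estimated for most participants. The documents do not support that: at exactly 80% dominant use, with independent reports, almost everyone would report both types. Clustered use of one type would raise the number of single-type reporters, but the documents do not describe that either.

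**Conclusion.** The point holds in a limited form. It is certain that a participant who reports one type gives no within-person information on the type slope, that eligibility permits such participants without limit, and that the plan has no provision for them. It is also clear from the text that the EMA mediator is not settled.

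The consequence is conditional. Under the assumed shares and variances, common-mean slopes recover 0.03 to 0.11 of a true 0.25 under the equal mix, and per-person slopes 0.04 to 0.17. With everyone at the most off-type use that eligibility allows, common-mean slopes recover 0.06 to 0.20. The direction is toward no mediation. A model with preference predicting the slope is about unbiased but, with centred type, has roughly 1.5 to 3 times the SD obtained with known slopes. These figures rest on independent reports, known variances and an invented distribution of shares, so they illustrate the effect and do not forecast it.

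A reader might extend this to Aim 3 as a whole. That is not supported: the laboratory mediators are analysed in separate models. The point should be fixed before the 6-month outcomes are analysed.

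**What to change.** 1. **Aim 3, Step 3.** Enter each participant's mean EMA rating of the preferred cigarette type as an EMA mediator. It adapts Aim 2 secondary outcome (a), which is not now restricted to the preferred type. It needs no off-type reports, and it matches the Study Objective's hypothesis that menthol smokers show greater appeal by EMA. State, before the 6-month outcomes are analysed, whether this mean or the slope is primary.
2. **If the type slope is kept.** Obtain it from an HLM with person-mean-centred cigarette type and with baseline preference predicting both the intercept and the type slope. Report by group how many participants reported both types and how many off-type reports they gave. Say that a null slope-based result will not be read as evidence against mediation when off-type reports are few.
3. **Optional sensitivity analysis.** Limit the slope analysis to participants with a pre-set minimum of reports of each type (for example 5), described as selected on behaviour during EMA. It may be small: about 39 of 250 under the assumed mix, and about 2, 21 or 135 if everyone is at 5%, 10% or 20% off-type.

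The cost is analysis-plan wording, with no new data. The main downside is that the mean rating is a between-person level. It carries individual rating style and is itself attenuated by measurement error, so it answers a somewhat different question from the within-person contrast.

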If a participant is recruited and enrolled when in-person data collection activities are limited or restricted due to COVID-19, online consent and online baseline survey will be offered in order to address current restrictions on in-person data collection. They will be asked to provide consent online (by electronically signing the consent document), complete the baseline survey online, and then begin the daily phone surveys immediately after that (Phase 2). See below for consenting process online. If the person would like to complete the smoking sessions in person, once in-person data collection can begin (Phase 1), a member of the research team will contact participants to determine if they are still interested in participating in Phase 1 in-person sessions, and determine if they are eligible to participate (e.g., still smoking, not currently pregnant/breastfeeding/planning to become pregnant). If they are interested and meet eligibility criteria, they will be scheduled for the 3 in-person laboratory sessions. We will make every effort to contact participants and schedule those sessions as soon as possible after they enrolled. Given the uncertainty of the COVID-19 outbreak, we cannot determine how long participants may need to wait. Additionally, remote smoking sessions will be offered to ensure data collection for individuals that are not comfortable with in-person visits or in the event they are unable to enter the laboratory setting. During the screener, participants will be asked if they would like to attend socially distanced in-person visits, or remote study sessions.

Study Products

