Study Cigarettes. Using procedures similar to Strasser and colleagues commercially available Camel Crush cigarettes (R.J. Reynolds, Winston-Salem) will be used for both menthol and non-menthol smoking in Visit 2.⁶ We chose these because they contain a small, menthol-filled capsule that breaks open when squeezed and releases menthol into the cigarette. They are well suited to isolate menthol’s effects because there is no menthol flavor prior to squeezing, minimal menthol variation after crushing, and similar levels of nicotine, cotinine, and NNK, before and after crushing. They are also ideal because they are not popular among our typical participants (i.e., < 1 in 125 participants), based on analysis of PATH Wave 1 data, and have nicotine levels comparable to the very popular brands of Newport (0.8 mg) and Marlboro (0.8 mg). Thus, Camel Crush cigarettes will allow us to isolate menthol’s effects in the absence of cigarette loyalty or familiarity, and the other potential differences between cigarette types other than menthol level.

Study Procedures

Phase 1 Overview and Experimental Design

Phase 1 (Aim 1) will take place in the laboratory at Health Promotion Research Center (HPRC), in Oklahoma City, OK. A 2 (menthol preference: yes/no) X 2 (cigarette type: usual brand versus experimental cigarette) factorial design will be used with cigarette type as a within-subjects factor. After determining initial eligibility via telephone and/or online, \geq 12-hour abstinent smokers (CO-verified \leq 8 ppm) will attend each of 3 lab visits scheduled around the same time of day and separated by at least 48 hours (from start time

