After completing questionnaires, ARV will be measured by having participants smoke their usual brand of cigarette (*ad libitum*), which they will be instructed to bring with them to the first study visit. They will smoke through a mouthpiece of the Cress Smoking Topography Device, during a 60-minute smoking Visit or the SODIM Smoking Puff Analyzer Mobile SPA-M The CReSS or SODIM instrument will record puff volume, duration and velocity and inter-puff interval for each puff and their aggregate averages.⁷⁻¹⁰ Puff topography measures will be used to examine whether increased puff volume, duration, and lower inter-puff interval differ across menthol and non-menthol cigarettes. Before and after smoking, heart rate and blood pressure will be collected (if session is taken in person); exhaled carbon monoxide (CO boost), and subjective response to smoking (craving reduction, psychological reward, satisfaction, sensory effects) using the Cigarette Evaluation Questionnaire (CEQ). Exhaled carbon monoxide will be collected and measured in ppm immediately before and after smoking. At the completion of Visit 1, participants will be paid for the visit, and scheduled for study visits (V2 and V3).

Laboratory Visit or Session 2: Sampling Experimental Cigarettes and Cross-Price Elasticity Task. Participants will confirm abstinence by being asked the last time they smoked a cigarette in addition to providing a carbon monoxide measurement (CO \leq 8 ppm). Visit/Session 2 (within-subjects) will familiarize participants with the experimental cigarette (Camel Crush) by having them take a minimum of 3 and up to 5 puffs each of a menthol and non-menthol version (counterbalanced) and complete subjective ratings,

smoking exposure (CO boost), and behavior (topography: total time smoked). There will be a 20 minute washout period between each cigarette smoked, per our consultant's ([name]) paradigm protocol¹¹⁻¹⁴. Before and after smoking heart rate and blood pressure will be recorded (if session is taken in person), approximately 5 minutes after smoking subjective response, and CO boost will be recorded. After another 20 minute wait period from the last cigarette puff.

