Using a concurrent schedule, participants will be able to switch from working on one screen to the other as often as they desire. Consistent with relative reinforcement paradigms, the reinforcement schedule in the non-menthol earning screen will remain constant at a fixed ratio FR-25 (25 targets achieved to earn a point) while the reinforcement schedule for the menthol cigarette will increase (require more effort) with a progressive ratio schedule of PR-25 x over 10 trials, such that 25, 50, 75, 100, 125, 150, 175, 200, 225, and 250 targets have to be "hit" to earn a point.

The choice task determines how reinforcing menthol cigarettes are relative to non-menthol cigarettes (of the same brand) by the participant's willingness to work increasingly harder for puffs of a menthol cigarette vs nonmenthol cigarette. Reinforcement will be defined by the breakpoint, or the highest trial (out of 10 trials) that will be completed for menthol cigarette puffs.

The computer task will be performed until 10 trials are completed and a total of 10 points (or puffs) are accumulated. Per paradigm protocol, cigarette puffs earned are taken at the end of the procedure.²¹ Following the choice task, participants will be able to smoke the cigarette puffs they earned (up to 10 puffs). As in Visits 1 and 2, subjective response (e.g., smoking satisfaction, craving reduction, psychological reward, sensory effects like throat hit), smoking exposure (CO boost), and behavior (topography: number of puffs, total time smoked) will be measured.

To ensure that choice task responses are based on reinforcer preference rather than departure from the laboratory, the choice task will be followed by a 30-minute wait in the laboratory (if the session is taken in person). If the session is taken remotely, there may not be a 30-minute wait period. During this 30-minute wait period, participants will be queried about potential reactivity (i.e., behavior change or increased awareness of behavior and attitudes) to the laboratory visits with a brief survey. They will then be given instructions for the EMA phase of the study (Phase 2). During this training, participants will complete a practice survey from their phone. They will be given a wallet sized reference card containing the date range of the monitoring period, the lab study phone number, and a paper copy of the EMA questions and response options.

Table 2. Phase 1 Measures and Schedule of Events Under Normal Operating Procedures

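### No rule keeps laboratory values taken in or after the outcome window out of the Aim 3 models for COVID-era enrollees who waited for in-person Phase 1; the phase-order term does not correct this, and session mode is in no model

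*Combined protocol and SAP*

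**What the plan says.** All references are to the combined protocol and SAP.

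**Order and waiting.** Under the COVID-19 methods in Study Design, people enrolled while in-person work is restricted consent and complete baseline online, then start EMA. Those who want in-person Phase 1 are contacted once it can resume, and staff then "determine if they are eligible to participate (e.g., still smoking, not currently pregnant/breastfeeding/planning to become pregnant". Staff undertake to schedule as early as they can, but no maximum wait is set: "Given the uncertainty of the COVID-19 outbreak, we cannot determine how long participants may need to wait".

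**Follow-up.** Phase 3 Overview ties the final survey to enrolment, at 6 months, and not to completion of Phase 1. Two Aim 3 primary outcomes, smoking days and number of cigarettes, cover the previous 30 days. Dependence and harm perceptions are taken at the survey itself.

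**Use of the laboratory measures.** Phase 3/Aim 3 Analyses regresses each 6-month outcome on its baseline level and demographics, then menthol status, then the laboratory or EMA measure. The laboratory measures are tested both for predictive validity and as mediators.

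**Adjustment.** The last line of Phase 2/Aim 2 Analyses reads: "Analyses will control for the order in which study phases were completed (e.g., Phase 1 vs Phase 2 first".

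**Mode.** At screening, "participants will be asked if they would like to attend socially distanced in-person visits, or remote study sessions". The topography device can differ by mode: "They will smoke through a mouthpiece of the Cress Smoking Topography Device, during a 60-minute smoking Visit or the SODIM Smoking Puff Analyzer Mobile SPA-M". At Visit 3 a 30-minute wait is imposed so that "choice task responses are based on reinforcer preference rather than departure from the laboratory", but "If the session is taken remotely, there may not be a 30-minute wait period". Neither the Aim 1 nor the Aim 3 covariate list includes mode.

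**The concern.** A predictor or mediator has to be measured before the outcome it is said to explain. With an open-ended wait and a fixed follow-up date, the plan permits (it does not intend) a laboratory value taken during the 30 days being reported on, or after the survey. Such a value may partly reflect the outcome and so look predictive when it is not. Because delayed participants are rechecked for current smoking, whether a late value exists at all also depends on smoking after enrolment.

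The main exposure is the predictive-validity test in Aim 3. The mediation criterion, a fall in the menthol coefficient, is affected much less.

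Mode is a secondary issue. It changes the setting and possibly the post-task wait, which bear on subjective ratings and the choice-task breakpoint (both primary in Aim 1). It also changes the topography and CO devices, which bear on secondary outcomes only.

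**Working it through.** **1. When is a visit late?** The plan gives no figure to reproduce. Inputs: 6 months taken as 183 days; 14 days of EMA first; a 30-day recall window; and, from Phase 1 Overview, "each of 3 lab visits scheduled around the same time of day and separated by at least 48 hours", so Visits 2 and 3 fall at least 2 and 4 days after Visit 1. Let w be the wait in days from the end of EMA to Visit 1.

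- The recall window opens on day 183 − 30 = 153.
- Visit 1 is in the window if 14 + w > 153, so w > 139. For Visits 2 and 3, w > 137 and w > 135.
- Visit 1 is after the survey if 14 + w > 183, so w > 169. For Visits 2 and 3, w > 167 and w > 165.

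Wider visit spacing lowers the thresholds for Visits 2 and 3. The documents set no limit below any of them.

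**2. What does a late value do to the predictor test?** The documents do not give the share affected, so this is an illustration. Simulated trials had n = 250 (125 per group), a menthol effect of 0.3 SD on the outcome and a true laboratory-measure effect of zero. A share of the laboratory values was replaced by values correlated 0.3-0.5 with the outcome. The model was outcome on baseline outcome, menthol and laboratory measure, with baseline/follow-up correlation 0.5-0.8. The result depends on how much of the late value's correlation is reverse influence and how much runs through baseline, which the model already adjusts for. Entries are rejection rates at a nominal 5%; with none late the rate was 4.8-5.1%.

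| Share late (of 250) | All reverse influence | Half through baseline | All through baseline |
|---|---|---|---|
| 5% (about 12) | 5.2-6.4% | 5.2-5.6% | about 5% |
| 10% (25) | 5.9-11.1% | 4.8-7.0% | about 5% |
| 20% (50) | 9.3-28.4% | 5.8-11.0% | about 5% |

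**3. Does the phase-order term help?** Every waiting participant is EMA-first, so the term shifts the mean for that group and leaves the link between late value and outcome inside it untouched. Rerunning the worst cell (20% late, all reverse influence) gave 28.8% with and without the term. In a separate run with half the sample assumed EMA-first, including everyone late, rates with the term were 5.8-10.4% (10% late) and 8.5-28.0% (20% late), against 6.2-10.4% and 8.5-27.7% without it.

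**4. Mediation criterion, all reverse influence.** If menthol does not shift the laboratory measure, the spurious fall in the menthol coefficient is within 0.03% of zero. If menthol shifts it by 0.3 SD, the fall is 1.1-3.8% (10% late) or 2.2-7.5% (20% late). With a 0.5 SD shift it is at most 12.6%.

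**5. Mode, between-group tests only.** Bias = (difference between groups in remote share) × (mode shift in SD). Type I error = P(|Z + bias/√(2/125)| > 1.96), with √(2/125) = 0.1265. Shifts of 0.2 and 0.5 SD are assumed.

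| Imbalance (points) | 0.2 SD | 0.5 SD |
|---|---|---|
| 0 | 5.0% | 5.0% |
| 10 | 5.3% | 6.8% |
| 20 | 6.2% | 12.4% |
| 30 | 7.6% | 22.0% |

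A constant mode shift cancels from within-subject contrasts for anyone who used one mode throughout.

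**The case against.** The late group requires several things at once: enrolment during restrictions, a preference for in-person sessions although remote ones are offered, and a wait of roughly four and a half months or more after EMA. The protocol also has procedures for in-person visits under COVID and a commitment to early scheduling. This stands: the share may be small, and no passage supports 20%. But these measures reduce the number without bounding it.

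A late value may correlate with the outcome only through stable dependence or preference, which baseline adjustment absorbs. This also stands, and is why the left-hand column of the first table is an upper case for the correlations chosen.

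The order term might be read as a stand-in for mode, since normal operations mean in-person and laboratory-first. It is at best a partial proxy: EMA-first participants who go remote and those who wait for the laboratory receive the same code. The Aim 1 and Aim 2 sections allow covariates linked to drop-out or missing data, so mode could enter that way, but neither names it.

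A reader might infer that mode confounds the menthol comparison. The documents do not support that: bias needs mode use to differ by preference group, and no passage suggests that it does. Nor do they say that the reason for the Visit 3 wait applies equally at home.

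**Conclusion.** The timing gap holds on the text. The wait is unbounded, follow-up is anchored to enrolment, and nothing removes late laboratory values from the Aim 3 predictor and mediator models. The phase-order term does not repair it.

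The size is uncertain. On the assumptions above, false positives run from about 5%, when baseline explains the late correlation, to at most 6.4%, 11% and 28% with 5%, 10% and 20% late, when all of it is reverse influence. The late shares and correlations are assumptions, not document figures.

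Two stronger readings should be resisted. One is that the Aim 3 mediation result is broadly invalid: the mediation criterion moves little even in the upper case. The other is that participants aged 18-20 enrolled before the Tobacco 21 exemption form a further late group: the documents speak of recruiting that age group and of proceeding with sessions 2 and 3, but do not say that those already enrolled were called back.

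The omission of mode is real but secondary, and its effect is conditional on an imbalance that has not been shown. Both points justify a change in SAP wording, made before results are seen.

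**What to change.** 1. In the laboratory-based Aim 3 models, let the primary analysis use only values from a visit (Visit 1 for absolute reinforcing value, Visit 2 for cross-price elasticity, Visit 3 for the choice task) before the 30-day recall window for past-30-day outcomes, or before the 6-month survey for dependence and harm perceptions. Either treat late values as missing under the plan's missing-data approach, saying explicitly that the imputation described under Aim 2 covers them, or use on-time complete cases. Report all values as measured as a sensitivity analysis. With 20% late, and lateness random or related to heavier smoking, simulated false positives were 8.5-28.2% as measured, 4.6-5.2% on-time complete case and 4.8-5.3% with imputation, so either choice is defensible.
2. Derive or record session mode at each visit. Add it as a covariate to the between-group Phase 1 models (for example absolute reinforcing value at Visit 1), with an in-person-only sensitivity analysis. In Aim 3, use it as a sensitivity analysis.
3. Report, by preference group, how many were measured late and how many remotely.

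The cost is SAP wording and, at most, one field per visit. Mode may be recoverable from the device used, the time-stamped home CO readings and the vital signs taken only in person. The downside is that a few measured laboratory values are set aside in the primary models; imputing them assumes missing at random given the data in the imputation model.
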